## EXPECTED BENEFITS

Describe both the expected benefits to individual subjects participating in the research and the importance of the knowledge that may reasonably be expected to result from the study. Provide a brief, realistic summary of potential benefits to subjects, for example, "It is hoped that the treatment will result in a partial reduction in tumor size in at least 25% of the enrolled subjects." Indicate how the results of the study will benefit future patients with the disease/condition being studied and/or society, e.g., through increased knowledge of human physiology or behavior, improved safety, or technological advances.

There are no direct known benefits to study volunteers from the study. However, there is the prospect of direct benefit to study volunteers as they may have improved bone density and bone microarchitecture after study treatment. This research may lead to an improved understanding of the disordered bone metabolism in teenage girls with AN and whether administration of IGF-1, a key bone anabolic factor, with low-dose estrogen therapy, is effective in increasing peak bone mass in this population compared with estrogen alone. The potential benefits are thought to warrant the risks described above.

## EQUITABLE SELECTION OF SUBJECTS

The risks and benefits of the research must be fairly distributed among the populations that stand to benefit from it. No group of persons, for example, men, women, pregnant women, children, and minorities, should be categorically excluded from the research without a good scientific or ethical reason to do so. Please provide the basis for concluding that the study population is representative of the population that stands to potentially benefit from this research.

All subjects will be female as the vast majority of patients with AN are female. We will be recruiting adolescents and young women 14-22 years old as there have been no treatment thus far has been successful in increasing bone density in adolescent girls with anorexia nervosa.

When people who do not speak English are excluded from participation in the research, provide the scientific rationale for doing so. Individuals who do not speak English should not be denied participation in research simply because it is inconvenient to translate the consent form in different languages and to have an interpreter present.

People who do not speak English will not be excluded from study participation. PHRC policy on Obtaining and Documenting Informed Consent of Subjects who do not speak English will be followed. For this study, potential subjects will be given a written translation in a language understandable to them of the “short form” or of the entire English version of the consent form approved by the Partners Human Research Committee (PHRC).

For guidance, refer to the following Partners policy:

Obtaining and Documenting Informed Consent of Subjects who do not Speak English  
<http://healthcare.partners.org/phsirb/nonengco.htm>

○ Health care personnel for many of the suburban high schools and independent schools such as [name] in Concord, MA, [name] and [name] for Milton Pediatrics in Milton, MA, as well as various pediatric primary care practices in the Boston community are contacted regularly and invited to attend as well.

(ii) The Eating Disorders Unit at Massachusetts General Hospital, which is the largest operating eating disorders clinic in New England. The Eating Disorders Unit in the Massachusetts General Hospital Child Psychiatry Service and the Adult Eating and Weight Center together form the largest outpatient Eating Disorders Clinic in the New England area. Since its inception in 1981, the Clinic has evaluated more than 4000 patients with AN and/or bulimia nervosa. Over 200 new patients are evaluated in the Clinic each year and over 150 patients are in treatment at any one time. Patients in the Clinic, many of whom were recruited for an ongoing, prospective, longitudinal study of eating disorders, are interested and willing to participate in research projects. In addition, Clinic patients have participated in studies of low bone density, obsessive compulsive symptomatology, childhood sexual trauma, and pharmacological treatment.

(iii) The Harris Center, previously the Harvard Eating Disorders Center, in which [name] is involved, brings together many of the eating disorders programs at Harvard Hospitals, including Deaconess Waltham Hospital. It also hosts annual dinners and sends out biannual newsletters that inform clinicians and families of eating disordered patients about new research opportunities. The Harris Center is a national non-profit organization whose goal is to promote the healthy development of women and others at risk through research, training, outreach and prevention. The Harris Center web-site is a frequently hit ED site, and details about the study will be available on that site. The Harris Center networks regularly with major treatment centers for eating disorders in Connecticut, Vermont, Rhode Island, New Hampshire, and Maine and with the 250 college health centers in the Greater Boston area;

(iv) Walden Behavioral Care. The Neuroendocrine Unit is invited to give monthly educational talks to patients and provide information about ongoing studies at the inpatient, partial hospitalization and residential programs. The service admits about 280 in- and outpatients with eating disorders each year

(v) The Massachusetts Eating Disorders Association, which runs support groups for women and teenagers with eating disorders throughout eastern Massachusetts;

(vi) Health services at local colleges and universities such as Harvard University, Massachusetts Institute of Technology, Boston University, Boston College, Brandeis University, Emerson College, and Wellesley College

(vii) Facebook Advertisements. We also plan to use Facebook advertising to reach potentially interested subjects living in the Boston area. Women ages 18-45 living in New England will see advertisements for this research study in the "News Feed" section of their Facebook and be directed to an IRB approved RedCap prescreen survey. These advertisements will in no way be

designed to target individuals who indicate they may be struggling with an eating disorder on Facebook. The ads are shown to individuals based on the demographic requirements but have no link to any specific personal, profile or browsing history information. Examples of these advertisements are attached to this study protocol in Insight. A general Facebook page has also been created for this study (a Facebook requirement) and includes only basic contact and study information. A copy of this page is also attached to this study protocol in Insight.

(viii) Hasbro Children's Hospital at Rhode Island Hospital. We work with [name] and her team of providers to recruit subjects from Hasbro. This recruitment site will also function as an offsite clinic for follow up visits to provide Hasbro patients the opportunity to participate in the study with greater convenience. Subjects who are interested in the study can complete the eligibility portion of the screening visit at Hasbro and come to MGH for the consent process and baseline, 6 month, and 12 month visits. They will have the option to complete the entire 1, 3, 4.5, 7.5, 9, and 10.5 month visits at Hasbro.

To maximize enrollment of adolescent subjects with AN, a number of referral mechanisms have been put into place over the past year that utilize the collegial relationships between [name], [name] and various directors of area eating disorder programs, as well as the Head of Child Psychiatry and major pediatric primary care practices. The investigators attend a monthly eating disorders support group at Walden Behavioral Care, which typically has an attendance of 70-80 patients, families, health professionals, and educators. The investigators also give talks on the endocrine and metabolic complications of AN to patients on the inpatient eating disorders units at Walden Behavioral Care, Center for Eating Disorders at Cambridge, Laurel Hill and HRI on a monthly or bi-monthly basis. Additionally, the Neuroendocrine Unit at Massachusetts General Hospital, in collaboration with the Harris Center, sponsors primary care symposia annually to educate the primary care clinician about eating disorders. These sessions also inform clinicians about research opportunities for eating disorder patients.

Control subjects will be recruited from pediatric practices at MGH, MGH-affiliated health care centers and community practices. Recruitment will occur through collaboration with physicians and caregivers at the above centers, and advertisement (i.e. posters, newsletters, and papers) in the community.

All subjects 18 years and older, and guardians of subjects younger than 18 years will sign an approved consent form, and all subjects 14-17 years old will sign their assent in this PHRC-approved Consent Form detailing study procedures. The consent and assent forms will be read to subjects and their guardians and signed in the presence of the study investigator. Minor subjects who turn 18 years of age during the course of the study will be asked to sign the approved consent form as an adult. In cases where the parents live out of state and find it difficult or inconvenient to come to Boston, we will ask the IRB for an exception to the protocol such that the study can be explained to parents and subjects over the phone and consent forms mailed/faxed to the parents/subjects to sign and send back to us. We will conduct the consent interview by telephone when the parent can read the consent as it is discussed. PHRC policy on Obtaining and Documenting Informed Consent of Subjects who do not Speak English will be followed. Potential subjects will be given a written translation in a language understandable to them of the "short form" of the consent form or of the entire English version of the consent form approved by the PHRC.

Psychologist co-investigators who obtain consent from subjects, if they are also treating psychologists, will not recruit their own patients for the study.

2) Subjects will also be recruited by using a REDCap survey, where all email correspondence will be done using encryption, as per institutional policy. Subjects can express

interest in the study by sharing their contact information and filling out eligibility criteria by using this survey.

Provide details of remuneration, when applicable. Even when subjects may derive medical benefit from participation, it is often the case that extra hospital visits, meals at the hospital, parking fees or other inconveniences will result in additional out-of-pocket expenses related to study participation. Investigators may wish to consider providing reimbursement for such expenses when funding is available

AN subjects will receive \$90 for completing each outpatient visit, except for the screening visit. AN subjects will also receive \$50 each for completing the optional Baseline and 12 Month MRI, as well as reimbursement up to \$25 per visit for parking and/or transportation costs to MGH. Healthy subjects will receive \$100 for completing the study visit, as well as reimbursement up to \$25 for parking and/or transportation costs to MGH. AN subjects can receive up to \$910 for completing this study and its MRI sub-study, and healthy subjects can receive up to \$100.

For guidance, refer to the following Partners policies:

Recruitment of Research Subjects

<http://healthcare.partners.org/phsirb/recruit.htm>

Guidelines for Advertisements for Recruiting Subjects

<http://healthcare.partners.org/phsirb/advert.htm>

Remuneration for Research Subjects

<http://healthcare.partners.org/phsirb/remun.htm>

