Subjects who do not live locally will be able to have their blood drawn offsite for levels of IGF-1 and bone markers. Subjects who choose this option will also have a history and physical performed by a local physician for each offsite visit. Tests that need to be run in real time will be done at local laboratories, with the results mailed to investigators. Otherwise, the samples will be mailed to investigators.

Subjects who are in residential treatment can have their visits at the treatment center with permission from the center, the subject's case manager, and the subject. The consent, history, and physical will be done by licensed study staff. This applies to all visits except for baseline, 6 month, and 12 month. Blood will not be drawn at the treatment center by study staff. If lab results are available for any labs that we need for the particular visit, we will use those labs. A release of information will be signed by the subject prior to obtaining any labs.

For studies involving treatment or diagnosis, provide information about standard of care at Partners (e.g., BWH, MGH) and indicate how the study procedures differ from standard care. Provide information on available alternative treatments, procedures, or methods of diagnosis.

No treatment thus far has been successful in increasing bone density in adolescent girls with anorexia nervosa. Weight gain is associated with some increase in bone density, but is difficult to attain (occurs in only 50%) and sustain. There are currently no FDA-approved therapies for anorexia nervosa-induced bone loss.

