Sample Size Determination: The study is powered to our primary endpoints, (i) change in lumbar spine BMD (specific Aim 1A), and (ii) change in trabecular bone density (specific Aim 3A) in girls with AN who receive estrogen and rhIGF-1 versus estrogen alone. **Specific Aim 1A:** The primary analysis for this Specific Aim and the study is to compare the change in BMD over time in subjects with AN randomized to receive rhIGF-1 and estrogen (n=50) with the corresponding change in estrogen treated subjects (n=50). Using data from our previous study, we found that the variance covariance matrix of the random effects model was as follows: variance-intercept 0.01056, variance-slope 0.001523, covariance -0.001, and the residual variance around each subject's trajectory 0.000533. Based on these parameters, with 100 subjects with AN (50 in each group), we will have an 80% chance of detecting a significant (p=0.05 two sided) difference in change in lumbar spine BMD between girls who receive estradiol and rhIGF-1 versus estradiol alone if the true difference in slope between the groups is 0.03 g/cm²/year. This is a medically significant difference in that lumbar spine BMD in adolescents with AN is about 0.08 g/cm² lower than that in healthy adolescents at baseline. Estradiol alone has a net effect of 0.02 g/cm².year in increasing bone density, so an additional effect of 0.03 g/cm² (with rhIGF-1) added to 0.02 g/cm² (from estradiol alone) would be a net effect of 0.05 g/cm²/year (from estradiol and rhIGF-1). This would allow girls with AN to catch up to healthy adolescents. The sample size calculation, which assumes a 20% dropout rate, is based on the methods described by Yi and Panzarella (38) using the program <http://hedwig.mgh.harvard.edu/biostatistics/node/35>. The same model can be used with covariates and possible mediators of treatment effects such as baseline nutritional status, body composition, hormonal status, exercise and pubertal maturation. We will also explore the possibility that effects of rhIGF-1 with estradiol persist after discontinuation of treatment by examining bone density 12 months after stopping therapy.

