Specific Aim 2B. The goal of this specific aim is to determine prospectively changes in bone microarchitecture and bone strength in girls with AN who receive rhIGF-1 and estrogen therapy (n=50) compared with changes in AN receiving estrogen alone (n=50). Bone microarchitecture will be assessed using HR-pQCT and bone strength using FEA at baseline, six, 12 and 24 months of the study. Our second primary study endpoint is the change in trabecular bone density in the two treatment groups over the course of the study. With 100 subjects (50 in each group) we will have an 80% chance of detecting a significant difference ($p=0.05$ two sided) in change in trabecular bone density in girls with AN who receive rhIGF-1 and estrogen compared with estrogen alone if the true relative change is 3.5% over the 12 month period. This assumes a standard deviation of relative change of 6%, as was found in the group of AN women who gained weight in a study by Milos *et al* (39). To understand the clinical meaning of such a change we note that AN women had a 20% decrease in trabecular bone density compared to normal women. The analysis will be accomplished using a longitudinal mixed model ANOVA with a random patient and time (slope) effect. The measure of interest will be the group time interaction. We estimate a 20% dropout rate based on our previous study. A secondary analysis will be a joint model with weight gain as described for Specific Aim 1. We will also compare changes in total cross-sectional area, cortical thickness, TbN, TbTh and TbSp between AN receiving rhIGF-1 and estrogen with AN receiving estrogen alone. Although this is not a specific aim, it will be interesting to compare the changes in BMD with the change in bone strength. An issue is that BMD and bone strength are measured in different units. In order to make the comparisons understandable, we will transform both to percent predicted using the data from healthy adolescent girls. Then we will fit a joint model for both measurements to assess the relationship between the two and which measure is affected most by treatment. In addition, we will examine these endpoints 12 months after stopping therapy to determine whether effects persist after discontinuing combination therapy. When comparing with healthy adolescent girls, we will adjust for multiple comparisons. Both unadjusted and multiplicity adjusted analyses will be presented.

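### Neither primary slope model commits to a baseline covariate; prespecifying baseline BMI by time would cost almost nothing and could add some precision

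*Protocol*

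**What the plan says.** **Who is recruited.** The Protocol's list of recruitment sources covers several levels of care. Item (iv) says the investigators' unit gives talks to patients and can "provide information about ongoing studies at the inpatient, partial hospitalization and residential programs". Item (ii) names a large outpatient eating disorders clinic, item (vi) names "Health services at local colleges and universities", and item (vii) adds Facebook advertising. Research Design and Methods also allows for participants who are in residential treatment. The inclusion criteria admit atypical AN with significant weight loss and set no BMI limit for AN girls, whereas controls must lie within a BMI percentile window. Randomization is by the research pharmacy, with no stratification factor stated.

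**Weight and bone.** The Protocol's standard-of-care text says "Weight gain is associated with some increase in bone density", and that this gain is achieved in only 50%. Its Specific Aims list BMI among the predictors of bone mass, in a cross-sectional aim.

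**The primary analyses.** SAP Specific Aim 1A compares BMD change between arms with a random-effects model and names no covariate for the primary test. It adds: "The same model can be used with covariates and possible mediators of treatment effects such as baseline nutritional status", followed by body composition, hormonal status, exercise and pubertal maturation. Specific Aim 2B uses a mixed model with random patient and slope effects for trabecular density and states "The measure of interest will be the group time interaction". It also plans a secondary joint model with weight gain, referring back to Aim 1, where no such model is described. By contrast, Specific Aim 2C commits to controlling for nutrition, pubertal status, hormonal status and exercise. Care setting is not mentioned in the SAP.

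**The concern.** Girls entering at different weights and levels of care may gain bone at different rates whichever arm they are in. Any part of that variation that can be predicted at baseline can be removed from the standard error of the treatment contrast, provided the model is fixed in advance. As written, the SAP leaves it there.

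The permissive wording has a second cost. It does not say whether the adjusted or the unadjusted model is primary, or which covariates would enter. It also groups baseline covariates with mediators, which are measured after randomization and do not belong in a precision adjustment. The choice could therefore be made after the data are seen.

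**Working it through.** **Inputs from the SAP.** "with 100 subjects with AN (50 in each group"); "80% chance of detecting a significant (p=0.05 two sided) difference in change in lumbar spine BMD"; slope difference 0.03 g/cm²/year; intercept variance 0.01056, slope variance 0.001523, covariance −0.001, residual variance 0.000533; 20% dropout. For trabecular density: 3.5% difference in relative change, SD 6%. **From the Protocol:** on-treatment scans at 0, 6 and 12 months. **Assumed:** R², the share of slope variance (BMD) or change variance (trabecular) that baseline covariates explain.

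**1. The SAP's BMD power.** With visits at 0, 0.5 and 1 year, Sxx = 0.25 + 0 + 0.25 = 0.5.
- Per-girl slope variance: 0.001523 + 0.000533/0.5 = 0.002589. The between-girl part is 0.001523/0.002589 = 59%; only this part can be explained by a covariate.
- No dropout: SE = √(2 × 0.002589/50) = 0.01018; power = Φ(0.03/0.01018 − 1.96) = 83.8%.
- 10 per arm leaving after month 6, partial data kept: sum the generalised least squares information over 40 girls with three visits and 10 with two, using V = ZGZ′ + 0.000533·I with G the stated matrix. This gives SE = 0.01078 and power = Φ(2.784 − 1.96) = 79.5%.
- 40 completers per arm only: SE = √(2 × 0.002589/40) = 0.01138; power 75.1%.

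The second dropout treatment reproduces the stated 80%, so 79.5% is the base used below.

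**2. BMD with covariate-by-time adjustment.** Replace 0.001523 by 0.001523 × (1 − R²) and repeat the 79.5% calculation.

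| Assumed R² | SE | Power |
|---|---|---|
| 0 | 0.01078 | 79.5% |
| 5% | 0.01062 | 80.6% |
| 10% | 0.01047 | 81.7% |
| 20% | 0.01015 | 84.0% |

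**3. Main effect only.** A baseline covariate without a time interaction reduces the intercept variance, not the slope variance. Cutting the intercept variance by 10% or 30% leaves power at 79.5% (83.8% with complete data). The by-time term does the work.

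**4. Trabecular density.** Treated as a two-group comparison of change, SE = 6 × √(1 − R²) × √(2/n) and power = Φ(3.5/SE − 1.96).

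| Assumed R² | SE, 40 per arm | Power, 40 per arm | Power, 50 per arm |
|---|---|---|---|
| 0 | 1.342 | 74.2% | 83.1% |
| 5% | 1.308 | 76.3% | 84.9% |
| 10% | 1.273 | 78.5% | 86.7% |
| 20% | 1.200 | 83.1% | 90.3% |

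The gains look larger than for BMD partly because R² here applies to the whole change variance, and the 40-per-arm column discards dropouts' partial data.

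**5. How much care setting might explain (illustration only).** If a share p of girls come from intensive programs and their BMD slope is higher by D, setting explains p(1 − p)D²/0.001523 of the slope variance. With p = 30% and D = 0.02, that is 0.21 × 0.0004/0.001523 = 5.5%; with D = 0.03 it is 12%. Neither p nor D is in the documents, and D = 0.03 equals the whole treatment effect targeted.

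**The case against.** **The documents do not show that entry BMI or setting drives the slope.** A reader might infer that a known determinant of BMD gain has been left out. The Protocol links bone density to weight gain, which happens after randomization, and lists BMI only as a cross-sectional correlate of bone level. Nor does it describe the recruiting programs' treatment as refeeding or say what share of girls will come from them; the item on inpatient and residential programs describes outreach. That baseline BMI predicts the slope is plausible but inferred. This objection stands, and it is why no single gain can be claimed.

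**The stated power may already contain this heterogeneity.** The variances come from the investigators' previous study with no covariates mentioned. If that population was similar, the 80% already reflects unadjusted variation. This stands for BMD, so the trial should not be called underpowered on this ground. For trabecular density it is less certain, since the 6% SD comes from women who gained weight.

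**Chance imbalance.** A reader might count a chance difference between arms in care setting as a further harm. If 30% came from intensive programs, arms of 50 would differ by at least 10 points in about 33% of randomizations. With D = 0.03, a 10-point difference moves the estimate by 0.10 × 0.03 = 0.003. But that is only about 0.3 standard errors (0.003/0.0102), and the unadjusted standard error already covers it. The unadjusted estimate remains unbiased with valid type I error.

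**Covariates are already allowed for.** They are, but permission is not prespecification, and the list mixes them with mediators.

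**The SAP expects short-term weight change not to affect the treatment difference (Specific Aim 2C).** That concerns whether the effect differs or is mediated. A covariate can sharpen an estimate without modifying the effect.

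**Conclusion.** The point holds as a low-cost improvement. Both primary slope models lack a committed baseline covariate, in a population recruited across levels of care with no stated BMI limit. The benefit is precision. For assumed R² of 5% to 20% it is about 1 to 4.5 points of BMD power (79.5% to between 80.6% and 84.0%) and about 2 to 9 points of trabecular power at 40 per arm (74.2% to between 76.3% and 83.1%). If R² is near zero the gain is near zero, and so is the cost.

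These figures rest on the SAP's own variances, dropout after month 6 for BMD, completers only for trabecular density, and an R² that the documents do not supply. They do not show bias, an invalid test or an error in the 80% stated for BMD.

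**What to change.** Before unblinding, amend SAP Specific Aims 1A and 2B so that the primary model for each endpoint includes baseline BMI both as a main effect and by time. State that on-study weight is not in the primary model, and separate baseline covariates from mediators in the sentence that now lists them together. Report the unadjusted model for each endpoint as a sensitivity analysis.

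Care setting at entry is an optional second covariate, also as a main effect and by time, but only if it is defined and recorded before randomization. Level of care is not among the listed screening or baseline items, so it would need a definition and a new field.

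For BMI the cost is SAP wording and two extra parameters per model with 100 girls. Height and weight are already measured at the baseline visit.
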